## 11.0 Data Management\* and Confidentiality

11.1 Since this study involves multiple repeated-measures over time, dealing with an ordinal level dependent variable, a Friedman's ANOVA would typically be used for data analysis. However, at least one previous study has analyzed this measure via parametric statistics, so we could potentially also pursue a Repeated Measures ANOVA if our data meets all parametric assumptions. Since our alternate hypothesis is two-tailed, our p-value will be divided by two for accurate significance assessment

11.2 To the investigators' knowledge, there is no previous literature examining the effects of an activity/intervention on a within-subjects change in performance on the FSD test. As a result, no within-subjects effects sizes were available for an a priori power-analysis for required sample size. In previous work examining the inter-rater reliability of the FSD test, Park, et al. used an effect size of 1.26, based upon the work of Rabin and Kozol, in which they measured the amount of ankle dorsiflexion and compared groups scoring differently on the FSD test in this anthropometric measure. We therefore, used 0.5 as our effect size because the current study design differs from the Rabin and Kozol study design, and given their large effect size the investigators felt justified in setting a moderate effect size for the power analysis. The power analysis used an alpha of .05 and power of .80 for a two-tailed hypothesis via a repeated measures, within factors ANOVA analysis. This power analysis determined the need for nine participants. With 37 students in the class, we have more potential participants than needed to ensure the required power to observe a statistical result if it exists.

11.3 The Excel sheet will be kept in in a password protected file on password locked computers in the PI and co-investigator's offices. Consent forms will be secured in a locked file cabinet in the PI's office.

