## 20.0 Resources Available

20.1 Both investigators have completed orthopaedic residencies and hold current licenses to practice physical therapy in the state of Louisiana. The co-investigator is an Orthopaedic Clinical Specialist, and the PI has recently taken the Orthopaedic Clinical Specialist exam and is awaiting results. PT licensure includes indications and contraindications for maximal exercise testing and prescription for various healthy and unhealthy populations. In addition, the PI has experience working with exercise testing at the Pennington Biomedical Research Center in Baton Rouge, LA. The co-investigator is currently completing his PhD work in Physical Therapy.

20.2 Describe other resources available to conduct the research: For example, as appropriate:

- The class of 2020 that will be enrolled in Exercise Physiology has a total of 37 students. With nine participants needed per the power analysis, there should be no difficulty recruiting the necessary number of participants.
- Both investigators are instructors in the School of Allied Health Professions in the Department of Physical Therapy, and have 30% of their time set aside for research purposes. This time will include recruitment and consenting of participants, testing, data analysis, and writing results for publication.
- The Faculty Practice Clinic in the School of Allied Health Professions is a functioning outpatient physical and occupational therapy clinic. It includes treadmills for aerobic testing, and the appropriate equipment to perform the FSD test. It also includes the emergency equipment necessary to be a functional clinic within regulation.
- The School of Allied Health Professions is part of the larger Health Sciences Center campus. Emergency transportation is available to the hospital, which is adjacent to the Medical School portion of campus. In addition, students have mental health services available for free through the School should this be necessary if a participant has an adverse psychological event to the testing procedures.
- All participants will give voluntary informed consent, by which they will be educated on what tests they will be expected to perform. Both investigators will be able to consent participants into the study. Both investigators will review the protocol prior to the testing sessions, and will keep independent records of FSD test. Prior to each testing sessions, the investigators will clarify any questions regarding

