22.5 N/A

### **23.0 Local Number of Subjects**

23.1 One hundred percent of the subjects will be recruited locally. As stated in the inclusion/exclusion criteria, participants will be included for post-testing only if they achieve  $\pm 10$ bpm of their predicted maximum heartrate on the Bruce protocol. Participants will be informed of the study, screened, and consented to participate at one time. During testing, participants will be gathered until adequate power is reached.

23.2 The physical therapy class the participants will be drawn from has 37 students total. All willing participants will be screened and consented for inclusion, and data will be gathered until adequate power is reached.

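### Nine participants is the number for .80 power with repeated-measures ANOVA; power for Friedman's test, named first, is not shown and may be well below .80

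*Protocol*

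**What the plan says.** Section 11.1 describes the FSD score as ordinal and measured repeatedly, and says that a Friedman's "ANOVA would typically be used for data analysis". It then adds that a repeated-measures ANOVA could also be pursued, provided the data meet all parametric assumptions.

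Section 11.2 gives the sample size: "The power analysis used an alpha of .05 and power of .80 for a two-tailed hypothesis via a repeated measures, within factors ANOVA analysis". The effect size is 0.5, called moderate, with no metric named. The result is stated as "This power analysis determined the need for nine participants". No power is given for Friedman's test. No within-subject correlation or sphericity value is given for the ANOVA.

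Section 20.2 repeats the number: "With nine participants needed per the power analysis, there should be no difficulty recruiting the necessary number of participants". Section 23.2 says that "data will be gathered until adequate power is reached", without saying what figure adequate power corresponds to.

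**The concern.** A sample size supports a power claim only for the test it was calculated for. On normal data Friedman's test is less efficient than the ANOVA F test because it uses only the ranks within each participant, and with four measurements the loss is not trivial. The protocol puts Friedman first because the outcome is ordinal, so the test most likely to be run is the one without a power figure.

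Nine is the only target in the protocol. If the study closes at or near nine and Friedman's test is not significant, the result could be read as a negative finding from a study with 80% power. Under some plausible inputs the real figure is nearer 65%, even if the assumed effect size is accepted.

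**Working it through.** **Inputs from the protocol.** Alpha .05, target power .80 and effect size 0.5 (section 11.2). Four measurements: one before and three after the treadmill test (sections 7.1 and 9.3).

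**Assumptions, because the protocol is silent.** Effect size read as Cohen's f; within-subject correlation ρ varied from 0 to .7; sphericity and normal data unless noted.

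**Step 1: reproduce nine.** For a within-subject factor with m measurements and N participants, the noncentrality is λ = f²·N·m/(1−ρ), with m−1 and (N−1)(m−1) degrees of freedom.

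- ρ = .3, N = 9: λ = 0.25 × 9 × 4 / 0.7 = 12.86, df 3 and 24, power .800. Nine is reproduced.
- ρ = .5, N = 7: λ = 0.25 × 7 × 4 / 0.5 = 14.0, df 3 and 18, power .813. Seven suffices.
- ρ = .5, N = 9: λ = 0.25 × 9 × 4 / 0.5 = 18.0, power .922.

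Under sphericity and the stated inputs, nine is therefore the ANOVA number only near ρ = .3. It also arises at ρ = .5 with a sphericity value (epsilon) of .75: power .789 at eight and .847 at nine.

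**Step 2: Friedman at nine.** Power was simulated (at least 40,000 data sets per setting, compound symmetry, several mean patterns scaled to f = .5).

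| ρ | ANOVA N for .80 | ANOVA power at 9 | Friedman power at 9 |
|---|---|---|---|
| 0 | 13 | .63 | .48-.52 |
| .3 | 9 | .80 | .64-.66 (F approximation .68-.70) |
| .4 | 8 | .86 | .71-.77 |
| .5 | 7 | .92 | .80-.85 |
| .6 | 6 | .97 | .88-.91 |
| .7 | 5 | .99 | .95-.97 |

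The ranges cover the mean patterns and the choice of critical value. At ρ = .3, Friedman reaches .80 at about 12 participants (.81-.82).

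**Step 3: cross-check.** The asymptotic efficiency of Friedman relative to the F test, for normal data and four measurements, is 0.955 × 4/5 = 0.76. Nine ANOVA participants then correspond to 9 / 0.76 = 11.8 for Friedman, which agrees with about 12.

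**Step 4: sensitivity.**

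- *Half-point scores on the 0-6 scale, with tie correction:* Friedman at nine has .66-.70 at ρ = .3 and .81-.85 at ρ = .5. Coarse scoring does not change the picture.
- *Non-sphericity:* with an autoregressive pattern (epsilon .78, mean correlation .55), Friedman at nine has .74 to .91 depending on the mean pattern. With epsilon .67 and mean correlation .50 it runs from .59 to .93. The result can lie on either side of .80.

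**The case against.** The strongest counter-argument is that the shortfall is not established. A reader might infer that Friedman's test cannot reach .80 with nine participants. The documents do not support that, because it turns on a correlation they never give: at .5 or above, with the stated alpha and four measurements, Friedman reaches about .80 or more. Under non-sphericity some patterns also exceed .80, including one with a drop at one minute and recovery afterwards, which is the shape that the background section anticipates. This stands, and it limits the conclusion. It does not restore the protocol's figure: under sphericity, the correlation that rescues Friedman at nine makes nine the wrong number for the ANOVA, which would need seven.

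A reader might also infer an arithmetic error in the nine. There is none to show, since the figure can be reproduced. Nine can be reached by other routes, such as three measurements or alpha .025, but those conflict with the four FSD tests and the stated alpha, so they are not relied on here.

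A third inference would be that recruitment stops at nine. The protocol presents nine as the need, consents all willing students and names no cap. Nor does it firmly fix the test, since ANOVA remains a conditional option.

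Finally, a statistical analysis plan may exist. That does not remove the point, because the protocol performs the power analysis itself and names the test it used.

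**Conclusion.** The point holds in a limited form. The stated .80 belongs to repeated-measures ANOVA and does not carry over to the test that section 11.1 names first. Under sphericity, and at the correlation that reproduces nine (.3), Friedman's power at nine is about .64-.66, or .68-.70 with the F approximation: a loss of roughly 10 to 16 points. At correlation .4 it is about .71-.77 and at .5 about .80-.85. These figures rest on Cohen's f = .5, four measurements, alpha .05, sphericity and normal data. The correlation, the effect-size metric and sphericity are not settled by the protocol, so a range is the most that can be stated. The defect is a mismatch between sizing and analysis with the deciding inputs missing, and it should be corrected before the power claim is relied on.

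**What to change.** In section 11.2, redo the power statement for Friedman's test with four measurements. State the assumed within-subject correlation, the effect-size metric and the alpha. Replace the single .80 at nine with a range over the correlation, about .65 at .3 to about .80 at .5, and note that departures from sphericity can move it either way. Carry the restated figure into section 20.2, and into section 23 so that adequate power there refers to a defined number for a defined test.

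The cost is one calculation and a few sentences. If the investigators then choose a larger number, the 37 students in the class leave room: even the 12 or so needed at correlation .3 is about a third of the class (12/37 = 32%), with no new recruitment source.

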11.4 N/A

PROTOCOL TITLE: The Effect of Cardiovascular Fatigue on Performance of the Forward-Step-Down Test

11.5 Each investigator will track scores independently during the testing procedures, with a random number assigned to each participant recorded on the consent form and matched to the Excel data collection document. The results will be combined into a locked spreadsheet that will be stored on the PI's and co-investigator's laptops, which are both password protected. The only information collected that will be stored will be the patient's health screening and consent information which will be secured in a locked file cabinet in the PI's office, and the scores from the FSD test secured as stated. Following publication of the data, the informed consent documents will be retained for the requisite six years per HIPAA and LSUHSC-S IRB regulations. At this time, the records will be shredded. Both the PI and the co-investigator will have access to the data since the co-investigator will be responsible for statistical analysis of the data.

**12.0 Provisions to Monitor the Data to Ensure the Safety of Subjects\***

The Bruce protocol is utilized in the many clinical exercise stress tests, and therefore is considered minimal risk because it is not greater than normal risk/discomfort expected during routine physical examination. In addition, the participants must all meet ACSM criteria that determine them to be low risk to participate in vigorous exercise. Therefore, the Bruce and FSD tests are not considered greater than normal activity for the participants of the study. However, the potential adverse events of exercise do include cardiovascular events such as myocardial infarction and death. Therefore, these risks will be minimized as follows:

- Prior to consenting the participants, either investigator will give potential participants a health screen that will determine if they require a physician's clearance to undertake vigorous physical activity such as the Bruce protocol. Those who do need a referral will not be consented to participate until cleared by their physician if they still wish to participate. The screen is detailed by the American College of Sports Medicine (see Appendix A for the screening flow chart).
- Participants will wear a heart rate monitor that will ensure the investigators are able to confirm appropriate cardiovascular response to exercise. Heart rate will be measured prior to and during testing each minute during the Bruce protocol. An adverse reaction to a maximal exertion test such as the Bruce protocol is a decrease in heart rate with the same or increased work load.

**13.0 Withdrawal of Subjects\***

13.1 Participants will be withdrawn without their permission if they demonstrate adverse reaction during the Bruce protocol that necessitates termination of the protocol prior to volitional maximum effort, as well as if they experience musculoskeletal injury during any portion of the test. Participants will be withdrawn if pre-testing blood pressure/heart rate monitoring reveals

PROTOCOL TITLE: The Effect of Cardiovascular Fatigue on Performance of the Forward-Step-Down Test

abnormalities that contraindicate Bruce Protocol testing. Participants will also be withdrawn if they do not meet the heart rate threshold during the Bruce protocol.

- 13.2 If the test must be terminated during the Bruce, the treadmill will be stopped and the participant monitored for normalization of hemodynamics, or appropriate medical procedures will be followed if necessary. Should participants be withdrawn before completion of the post-test FSD test, their data set will be removed from the analysis.
- 13.3 Data from participants who do not complete the final FSD test will be removed. Since testing is complete after the final FSD test, no further collection will need to be completed and participants do not need to return to the clinic.

#### 14.0 Risks to Subjects\*

- 14.1 Risks from performing the Bruce Protocol include muscle soreness and musculoskeletal injury, both of which are temporary and non-life threatening. Musculoskeletal discomfort is reversible with discomfort expected to pass within days. Since the participants are students who would be performing the Bruce Protocol tests for classroom experience, there is minimal economic or time burden.

More serious risks are possible, with a less than one percent risk for myocardial infarction and death due to over-exertion. Historically, this risk has been shown to be acceptable while performing cardiovascular stress tests with an estimate of 3.58 infarcts per 10000 tests and 4.78 serious arrhythmias per 10000 tests. The risk of death was 0.5 per 10000 tests. However, cardiovascular stress tests are not performed in young, healthy populations because they are not deemed medically necessary for sports or activity participation. Therefore, these numbers represent adverse events that occur in the population that is recommended by a physician to undergo the cardiovascular stress tests. In this study, if a participant falls into a category that requires physician clearance before participating in exercise, they do not meet the inclusion criteria for this study.

In general the risk of death from sudden cardiovascular infarct during vigorous exercise remains low. The ACSM estimates one death per 1.5 million vigorous exercise training sessions in men, and one per 36.5 million hours of moderate-to-vigorous exercise in women. These numbers were drawn from participation in community gyms, where screening for exercise-risk does not always occur; therefore, the risk for these serious side effects is predicted to be lower due to the pre-test screening performed. Again, the risk noted above in the general population is most likely higher due to the careful medical screening that will occur as part of the inclusion criteria.

PROTOCOL TITLE: The Effect of Cardiovascular Fatigue on Performance of the Forward-Step-Down Test

14.2 There is no data regarding risks other than possible musculoskeletal discomfort from performing the FSD test. It is possible that injury may result from performing this test in a fatigued state but this is an unlikely risk.

14.3 N/A

14.4 N/A

**15.0 Potential Benefits to Subjects\***

15.1 Participants will be able to calculate their predicted  $VO_{2max}$  from the Bruce protocol data, which is useful for training purposes should the participants be aerobic athletes. Participants will also gain knowledge of their movement quality during the FSD test, which can be used to improve their deficits and potentially decrease injury risk. After data collection is complete, participants can contact the investigators to obtain their FSD test scores.

15.2 N/A

**16.0 Vulnerable Populations\***

The study does involve students of the university at which the investigators are instructors. The risk of coercion has been minimized by ensuring the participants give voluntary informed consent. In addition, the students participate in the Bruce protocol testing for one of their classes. Care was taken to select investigators who are not involved with grading of that class to ensure students do not perceive they are being coerced into participation in the study.

**17.0 Community-Based Participatory Research\***

Not applicable at this time; the goal of the investigators is to ultimately determine if the FSD test can be used as a screening tool for injury risk based on current fatigue levels. Should the study progress to that level, involvement with members of the community, such as coaches, will be included to determine if this is a feasible screening tool.

**18.0 Sharing of Results with Subjects\***

18.1 Should cardiovascular abnormalities be discovered in the heartrate and blood pressure screenings prior, during, or after the testing, the participant will be informed of the importance of following up with the appropriate medical professional. If desired, the investigators will provide the participant with a letter detailing the findings.

**19.0 Setting**

19.1 Describe the sites or locations where your research team will conduct the research.

- Participants will be identified by the cohort who will be enrolled in Exercise Physiology (PHTH 7565) in the summer of 2018.

PROTOCOL TITLE: The Effect of Cardiovascular Fatigue on Performance of the Forward-Step-Down Test

- Research will be conducted at the School of Allied Health Professions Faculty Practice Clinic.
- N/A
  - N/A

## 20.0 Resources Available

20.1 Both investigators have completed orthopaedic residencies and hold current licenses to practice physical therapy in the state of Louisiana. The co-investigator is an Orthopaedic Clinical Specialist, and the PI has recently taken the Orthopaedic Clinical Specialist exam and is awaiting results. PT licensure includes indications and contraindications for maximal exercise testing and prescription for various healthy and unhealthy populations. In addition, the PI has experience working with exercise testing at the Pennington Biomedical Research Center in Baton Rouge, LA. The co-investigator is currently completing his PhD work in Physical Therapy.

20.2 Describe other resources available to conduct the research: For example, as appropriate:

- The class of 2020 that will be enrolled in Exercise Physiology has a total of 37 students. With nine participants needed per the power analysis, there should be no difficulty recruiting the necessary number of participants.
- Both investigators are instructors in the School of Allied Health Professions in the Department of Physical Therapy, and have 30% of their time set aside for research purposes. This time will include recruitment and consenting of participants, testing, data analysis, and writing results for publication.
- The Faculty Practice Clinic in the School of Allied Health Professions is a functioning outpatient physical and occupational therapy clinic. It includes treadmills for aerobic testing, and the appropriate equipment to perform the FSD test. It also includes the emergency equipment necessary to be a functional clinic within regulation.
- The School of Allied Health Professions is part of the larger Health Sciences Center campus. Emergency transportation is available to the hospital, which is adjacent to the Medical School portion of campus. In addition, students have mental health services available for free through the School should this be necessary if a participant has an adverse psychological event to the testing procedures.
- All participants will give voluntary informed consent, by which they will be educated on what tests they will be expected to perform. Both investigators will be able to consent participants into the study. Both investigators will review the protocol prior to the testing sessions, and will keep independent records of FSD test. Prior to each testing sessions, the investigators will clarify any questions regarding

PROTOCOL TITLE: The Effect of Cardiovascular Fatigue on Performance of the  
Forward-Step-Down Test

procedure to ensure the same progression of tests are performed on each participant.

### **21.0 Prior Approvals**

21.1 Permission will be obtained from the Exercise Physiology Course Coordinator to add the FSD test pre- and post-testing to the Bruce protocol laboratory experience.

### **22.0 Recruitment Methods**

22.1 Participants will be recruited from the physical therapy students enrolled in PHTH 7565 Exercise Physiology at the School of Allied Health Professions in the summer of 2018.

22.2 The participants will be from the DPT Class of 2020.

22.3 All students in the above class who do not meet the exemption criteria will be eligible.

22.4 N/A: an announcement will be delivered to the Exercise Physiology class regarding the experiment and consenting process.

